### 2.6 Subgroup Analysis

Three statistical tests will be performed for each subgroup. The treatment difference in the subgroup, the treatment difference for patients not in the subgroup and a test for interaction of subgroup status and treatment. The following are the planned subgroup analysis:

1. The primary outcome will be compared between treatment groups in the cohort of patients with pre-randomization  $\text{PaO}_2/\text{FIO}_2 < 120$  and in the cohort of patients with pre-randomization  $\text{PaO}_2/\text{FIO}_2 \geq 120$ .
2. Time from meeting ARDS severity criteria for study enrollment to randomization divided into two groups using the median value.
3. We will do a subgroup analysis using *routine use of NMB* in the study hospital as a grouping criterion. We will rank hospitals in terms of the number of sole exclusions for prior NMB use divided by the hospital's total enrollment. We will then form three roughly equal sized patient subgroups, based on the rank of their treating hospital.
4. We will conduct the required subgroup analysis of groups defined by race, ethnicity and gender.

## 2.7 Missing Data

Analysis is based on all available data with no imputation of missing data with a few rare exceptions which are noted in Appendix B. All our proposed analyses are valid under Missing at Random(MAR) data.

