### 2.3 Analysis Methods for: Secondary Outcomes, Descriptive Variables, Safety Outcomes, Patient Characteristics

Continuous secondary outcomes will be compared between treatment groups using a t-test. Ordinal secondary outcomes (defined as outcomes with ordinal levels such as none, mild, moderate...) will be compared between groups using the Cochran-Mantel-Haenszel ANOVA (row mean score) test. Categorical secondary outcomes will be compared between treatment groups using a Chi-square or Fisher's exact test as appropriate to the sparseness of the data. All tests will use a two sided p=0.05 significance level. There will be no correction for multiple comparison.

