## 2.8 Long Term Follow Up Data

Six month and one year survival, for each treatment group, will be calculated using a multistate model. Patients will be classified in terms of the following states, 1-Study Hospital, 2-Other Hospital, 3-Home 4-Dead, with possible transitions of 1-2, 1-3, 1-4, 2-3, 2-4. The time duration of each transition that is known will be calculated. Then this model will be used to estimate the 6 and 12 month survival, and its standard error for each treatment group separately[3]. The test of a treatment effect will then be the difference in the survival estimates divided by the pooled standard error. The method of estimation is based on the multiplication of probabilities. For instance, suppose a patient went home at 100 days but only has 120 follow up at the time of analysis or is lost to follow up at 120 days. Then the probability of death for this patient is probability of a transition from 3 to 4, for a patient who has been home for 20 days.

The primary analysis of continuous and ordinal follow up data on patient's functional status will be a comparison of the distribution of these data using the methods described in the analysis methods section 2.3. The primary issue with this choice of analysis is that the treatment difference is difficult to interpret if there is a mortality difference. In that case we will conduct several sensitivity analyses described below.

The problem is that we are measuring follow up variables, for instance the Euro QOL, denoted here as QOL, in some patients on the better treatment who would have died on the worse treatment. When there is a survival difference the simple comparison does not measure the potential harm or benefit of the intervention on QOL. What we seek to estimate, is the *survival average causal effect*, defined as the difference in QOL among patients who would have survived both treatments. We will assume that patients who would survive on the worse treatment will also survive on the better one. In that case, the mean value of QOL on the worse treatment among patients who would have survived on both treatments is just the ordinary mean of QOL on that treatment.

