To estimate the mean value of QOL on the best treatment among patients who would have survived both treatments, we need to take a weighted mean of QOL with weights equal to the probability of survival on the worst treatment given the value of QOL on the best treatment. Unfortunately, these weights cannot be estimated, but one can look at the difference in QOL on the two treatments as a function of how the weights are assigned in a sensitivity analysis. Note that our primary analysis assumes all these weights are equal.

We propose three sensitivity analysis of these variables ascertained among survivors. The first assumes that all the patients with the worst values of QOL would have died on the worst treatment. In terms of weights, all the weights are one except for the  $m$  worst QOL values where  $m$  is the difference of mortality rates on the two treatments. This was suggested by Permutt, T. and Li, F [4].

The second method is to assume weights of the form  $\exp(b Y)$ , where  $Y$  is QOL, and then vary  $b$ , note that  $b$  can be interpreted as the relative effect on mortality per unit  $Y$ . Finally, we can use weights based on patient covariates, using the model specified in the ALVEOLI Trial [5] to estimate the weights. For the first two analysis significance, will be tested by calculating the standard error of each mean. For the last, we can use the methods described by Hayden, Pauker and Schoenfeld [6]. In addition, in order to give a graphical representation of these data, one can use these methods to estimate the distribution, for instance the probability that  $Y < K$  in the better treatment which is the weighted mean of the indicator functions  $I(Y < K)$  weighted by the same weights described above. We will assume that if we are missing an observation for reasons other than death it is missing at random(MAR) if the proportion of patients missing in this way is high we will conduct a sensitivity analysis of the MAR approach.

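### SAP 2.7 says every analysis is valid under MAR, but the unadjusted available-case tests planned for long-term outcomes are not, in general

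*SAP*

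**What the plan says.** SAP 2.7 sets the general rule, "Analysis is based on all available data with no imputation of missing data with a few rare exceptions which are noted in Appendix B", and adds that "All our proposed analyses are valid under Missing at Random(MAR) data". (The imputation rules themselves stand in Appendix A3.)

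SAP 2.3 names the tests: "Continuous secondary outcomes will be compared between treatment groups using a t-test", and "Categorical secondary outcomes will be compared between treatment groups using a Chi-square or Fisher's exact test". Appendix A1 assigns one of these to each long-term outcome: disability, EQ-5D-5L, self-rated health, pain interference, PTSS-14, MoCA-Blind, AD8, and work, care use and residence. SAP 2.8 confirms that "The primary analysis of continuous and ordinal follow up data on patient's functional status will be a comparison of the distribution of these data", by the 2.3 methods. No covariate or earlier score enters.

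For non-response other than death, SAP 2.8 assumes MAR without naming the variables that it conditions on. It adds that "if the proportion of patients missing in this way is high we will conduct a sensitivity analysis of the MAR approach". The three sensitivity analyses that it describes in detail concern truncation by death.

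Protocol 6.4 collects these outcomes by telephone at 3, 6 and 12 months, with PTSS-14 at 6 and 12 only. SAP Appendix A3 records baseline values for ADL/IADL and EQ-5D-5L.

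**The concern.** MAR allows missingness to depend on anything observed, including baseline function and the score at an earlier call. A method is valid under MAR in general only if it uses that information, through a likelihood, imputation or weighting. A two-group test on responders discards it, so the sentence in 2.7 credits these tests with a property that they lack.

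This matters because non-response is a real prospect and may track health. Under SAP Appendix A3, self-rated health and pain are recorded only when the patient is available, and one incomplete question voids the MoCA total. Protocol 6.4.1 sets money aside to avert refusals. The treatment is unblinded (Protocol 5.1.1), and the trial measures weakness, stress symptoms and cognition because the arms might differ on them, so a response pattern that differs by arm is plausible, though not documented. At stake is the reading of the long-term secondary comparisons, each tested at two-sided 0.05 without multiplicity correction, and a validity statement that could be carried into the report.

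**Working it through.** **Plan figure used.** SAP 2.7 gives no number. The only plan figure needed is the total of 1408. A fixed design gives n per arm = [1.96√(2 × 0.31 × 0.69) + 1.2816√(0.35 × 0.65 + 0.27 × 0.73)]² / 0.08² ≈ 700.3, so 701 per arm and 1402 in total. With the three-look boundaries, 1408 gives power 0.90, as Protocol Table 1 states. At 1:1 allocation (not stated; assumed), survivors are 704 × 0.65 ≈ 458 in control and 704 × 0.73 ≈ 514 in the NMB arm.

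**Check 1: closed form.** Let X be an observed binary factor with prevalence 0.5, where X = 1 lowers the score by g SD. There is no true treatment effect. Let m₀ and m₁ be the missing rates at X = 0 and X = 1 within an arm. Among that arm's responders the share with X = 1 is

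π = (1 − m₁) / [(1 − m₀) + (1 − m₁)].

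The bias of the responder difference (NMB minus control) is −g(π_NMB − π_control). For a binary outcome with risks of 20% at X = 0 and 50% at X = 1, the bias in the risk difference is 0.30(π_NMB − π_control).

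| Missing at X=0 / X=1 | π control | π NMB | Bias, g = 0.5 | Bias, g = 0.8 | Risk difference |
|---|---|---|---|---|---|
| 15/35 in both arms | 0.433 | 0.433 | 0 | 0 | 0 |
| Control 20/20, NMB 15/25 | 0.500 | 0.469 | 0.016 SD | 0.025 SD | −0.9 points |
| Control 25/25, NMB 10/40 | 0.500 | 0.400 | 0.050 SD | 0.080 SD | −3 points |
| Control 35/15, NMB 15/35 | 0.567 | 0.433 | 0.067 SD | 0.107 SD | −4 points |

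Every row is MAR given arm and X. In simulation (2,500 trials per scenario) the t-test rejected a true null about 5% of the time in the first row and about 6 to 30% in the others; the chi-square test rejected about 6 to 20% in those other rows. Standardising over X returned 4.5 to 5.9% for the continuous outcome. Missingness that depends on arm alone also gives zero bias.

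Effect modification matters as well. Take the first row, with a true effect of 0.3 SD at X = 0 and none at X = 1. The true average is 0.15, but the responders give 0.3 × (1 − 0.433) = 0.17.

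**Check 2: earlier score as the driver.** Inputs, all assumed except the survivor count: 460 survivors per arm, correlation 0.7 between 3- and 6-month scores, no true effect, and logistic missingness at 6 months on the 3-month score. The bias is 0.7 times the between-arm difference in mean 3-month score among responders.

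| Slopes in the two arms | Bias at 15 / 25 / 35% missing | False rejection |
|---|---|---|
| −1 and −1 | 0 / 0 / 0 SD | about 5% |
| −0.5 and −1 | 0.04 / 0.07 / 0.09 SD | 7–8 / 13–15 / 19% |
| 0 and −1 | 0.09 / 0.15 / 0.20 SD | 26–27 / 52 / 72% |

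Ranges in the last column are the spread over repeat runs. Conditioning on the 3-month score left a bias of at most about 0.002 SD in every row.

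**Check 3: limit of the remedy.** If one arm's missingness instead depends on the current, unobserved score, which is MNAR, adjusting for the 3-month score still leaves about 0.07, 0.12 and 0.16 SD at 15, 25 and 35% missing.

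**The case against.** The strongest reply is that a randomised comparison of responders is sturdier than it looks. If poor health lowers response equally in both arms and does not modify the effect, the arm difference is unbiased. That stands, and it is why the range starts at zero. MAR could also be read narrowly as dependence on arm alone, and the tests then hold. But the trial observes baseline function and earlier scores, and the SAP does not state the narrow reading.

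The plan also has safeguards. Most instruments accept a proxy (self-rated health, pain interference and, in the protocol, PTSS-14 do not), incentives support response, and survival of those lost is checked against the National Death Index. These reduce missingness without making the sentence in 2.7 true.

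Four stronger readings are tempting, and none is supported:

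- A reader might infer that the long-term comparisons will be biased, or that the one-arm case is the expected size. The documents give neither missing rates nor a mechanism.
- A reader might infer that the 2.8 sensitivity analysis tests an approach that is never used. The SAP does apply available-case tests under a stated MAR assumption; what is absent is a threshold, a method and a variable list.
- A reader might infer that a repeated-measures model settles the matter. Check 3 shows that it does not if response depends on current health. Such a model can also extrapolate scores past death, which SAP 2.8 takes care to avoid.
- A reader might infer a threat to the primary result. The sample size and the fully followed primary outcome do not depend on these tests.

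**Conclusion.** The sentence in SAP 2.7 is wrong as written. The unadjusted available-case tests are valid only under conditions narrower than MAR: missingness unrelated to outcome within arm, or dependence on observed scores that is the same in both arms with no effect modification. Outside those conditions the size depends on how far the mechanisms differ by arm. Under Check 2's assumptions it runs from zero, through less than 0.1 SD for moderate differences, to about 0.2 SD in the extreme case. Missing rates, slopes, correlation and covariate effects are all assumptions. Confidence is high on the wording error and limited on magnitude. The point should be addressed, but it is confined to secondary long-term outcomes.

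**What to change.** 1. In SAP 2.7, replace the blanket claim with the conditions in the verdict.
2. For long-term outcomes, among patients alive at each visit, prespecify an analysis that conditions on data already collected: multiple imputation or a likelihood-based model using arm, baseline ADL/IADL and EQ-5D-5L where collected, baseline severity, and other-visit scores. Impute nothing after death.
3. Keep the simple tests alongside it, and leave the survivor analyses in SAP 2.8 unchanged.
4. Run the 2.8 missing-data sensitivity analysis whatever the missing proportion, with its method and variables named and an MNAR version that shifts the imputed scores by a range of deltas.
5. Before listing the PTSS-14 visits, reconcile Protocol 6.4 (6 and 12 months, no proxy) with SAP Appendix A3 (3, 6 and 12 months, subject or proxy).

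The cost is SAP wording and a little more standard analysis; no new data are needed.

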## 2.8 Long Term Follow Up Data

Six month and one year survival, for each treatment group, will be calculated using a multistate model. Patients will be classified in terms of the following states, 1-Study Hospital, 2-Other Hospital, 3-Home 4-Dead, with possible transitions of 1-2, 1-3, 1-4, 2-3, 2-4. The time duration of each transition that is known will be calculated. Then this model will be used to estimate the 6 and 12 month survival, and its standard error for each treatment group separately[3]. The test of a treatment effect will then be the difference in the survival estimates divided by the pooled standard error. The method of estimation is based on the multiplication of probabilities. For instance, suppose a patient went home at 100 days but only has 120 follow up at the time of analysis or is lost to follow up at 120 days. Then the probability of death for this patient is probability of a transition from 3 to 4, for a patient who has been home for 20 days.

The primary analysis of continuous and ordinal follow up data on patient's functional status will be a comparison of the distribution of these data using the methods described in the analysis methods section 2.3. The primary issue with this choice of analysis is that the treatment difference is difficult to interpret if there is a mortality difference. In that case we will conduct several sensitivity analyses described below.

The problem is that we are measuring follow up variables, for instance the Euro QOL, denoted here as QOL, in some patients on the better treatment who would have died on the worse treatment. When there is a survival difference the simple comparison does not measure the potential harm or benefit of the intervention on QOL. What we seek to estimate, is the *survival average causal effect*, defined as the difference in QOL among patients who would have survived both treatments. We will assume that patients who would survive on the worse treatment will also survive on the better one. In that case, the mean value of QOL on the worse treatment among patients who would have survived on both treatments is just the ordinary mean of QOL on that treatment.

To estimate the mean value of QOL on the best treatment among patients who would have survived both treatments, we need to take a weighted mean of QOL with weights equal to the probability of survival on the worst treatment given the value of QOL on the best treatment. Unfortunately, these weights cannot be estimated, but one can look at the difference in QOL on the two treatments as a function of how the weights are assigned in a sensitivity analysis. Note that our primary analysis assumes all these weights are equal.

We propose three sensitivity analysis of these variables ascertained among survivors. The first assumes that all the patients with the worst values of QOL would have died on the worst treatment. In terms of weights, all the weights are one except for the  $m$  worst QOL values where  $m$  is the difference of mortality rates on the two treatments. This was suggested by Permutt, T. and Li, F [4].

The second method is to assume weights of the form  $\exp(b Y)$ , where  $Y$  is QOL, and then vary  $b$ , note that  $b$  can be interpreted as the relative effect on mortality per unit  $Y$ . Finally, we can use weights based on patient covariates, using the model specified in the ALVEOLI Trial [5] to estimate the weights. For the first two analysis significance, will be tested by calculating the standard error of each mean. For the last, we can use the methods described by Hayden, Pauker and Schoenfeld [6]. In addition, in order to give a graphical representation of these data, one can use these methods to estimate the distribution, for instance the probability that  $Y < K$  in the better treatment which is the weighted mean of the indicator functions  $I(Y < K)$  weighted by the same weights described above. We will assume that if we are missing an observation for reasons other than death it is missing at random(MAR) if the proportion of patients missing in this way is high we will conduct a sensitivity analysis of the MAR approach.

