## 6.4 ASSESSMENTS AFTER HOSPITALIZATION

These domains and instruments to assess after hospitalization status were selected by the PETAL Neuromuscular Blockade Protocol Committee in conjunction with the PETAL Long-Term Outcomes Committee.

We will assess seven measures after hospitalization:

1. Disability: using Katz Activities of Daily Living (ADL)/Lawton Instrumental Activities of Daily Living Scale (IADL) plus two additional Nagi items
2. Health-Related Quality of Life (including utilities): EuroQol (EQ-5D-5L)
3. Self-rated health: 1 standard item
4. Pain-interference: 1 standard item
5. Post-traumatic Stress-like Symptoms: Post-Traumatic Stress Symptoms (PTSS-14)
6. Cognitive function: Montreal Cognitive Assessment (MoCA-Blind) or, via proxy, the Alzheimer's Disease 8 (AD8)
7. Subsequent return to work, hospital and ED use, and location of residence

These measures will be collected through telephone interviews with patients or their LARs (Appendix G). Informed consent process will include text to facilitate future ancillary long term follow up studies and data collection. All will be obtained at 3, 6, and 12 months except for post-traumatic stress-like symptoms, which will only be obtained at 6 and 12 months. All will be obtained in English or Spanish, from the patient wherever possible. Most will be obtained from proxies when necessary, except as noted for self-rated health, pain interference and post-traumatic stress-like symptoms.

The assessments after follow-up will provide information about post-discharge deaths faster than is available from other sources, although the National Death Index will be used to verify date of death whenever possible (see below).

The Katz ADL is associated with multiple health outcomes among community-dwelling elders[36], and valid among nursing home residents[37]. The Lawton IADL is probably the most widely used self-report or informant-report IADL instrument. These assess a range of common functional activities, from walking and toileting to managing money and cooking meals. We will use the precise wordings from the NIA-funded Health and Retirement Study for which US (and international) norms are available. These scales have been specifically shown to perform well when assessed by proxies for ICU survivors. [40] We will remove the 3 ADL/IADL items that are duplicative of the EQ-5D questions (using the EQ-5D instead), and will add two items from the Nagi scale [41]as implemented in the HRS.

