The EQ-5D[44] has US utilities[45] and is recommended for measurement of health-related quality of life among critical illness survivors.[46] It is quick and feasible in individuals with inattention and fatigue[47]. We will use the EQ-5D-5L version currently used by both the ANZIC RC in Australia and New Zealand and ICNARC in the United Kingdom. We will not use the Visual Analog Scale as these follow-ups will be phone administered and the VAS is not necessary for health economic analysis.

Self-rated health and pain-interference are two common single-item scales that are widely used. We will use the wordings from the SF-12. Because of the highly subjective nature of these domains, these will only be assessed by self-respondents.

The Montreal Cognitive Assessment (MoCA) appears superior to the mini mental status examination and its derivatives for neurocognition assessment in critical illness survivors [48-51], and allows rapid, reliable determination of cognitive impairment [52] in various clinical syndromes.[51, 53-55] The MOCA-Blind version is developed for phone administration. Among community-dwelling older individuals, MoCA scores were lower (more impairment) among patients with elevated levels of inflammatory cytokines. When patients are not able to respond themselves, the validated AD-8 [56]will be used to assess cognitive function by proxy.

We will capture return to work status using the Improving Care of ALI Patients (ICAP) study questionnaire.[59] The Improving Care of Acute Lung Injury Patients employment instrument (ICAP-12) was designed to determine pre- and post-morbid employment status in a multi-center observational study of ARDS survivors[59, 60] and used externally in the NHLBI ARDS Network's ARDS Long-term Outcomes Study (ALTOS) cohorts[61, 62]. We will also ask about recent hospital and Emergency Department use, and whether the patient is residing in a nursing home, at home, or elsewhere.

We will also verify duration of survival for patients lost to follow-up or noted to have died using the Centers for Disease Control and Prevention's National Death Index (NDI) and other federal databases. We will use each patient's social security number (SSN) for an exact NDI match.

We will also collect the patient's Medicare identification number for patients in Medicare to allow assessment of post-discharge health care utilization without any respondent burden back on the

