## B TIME-EVENTS SCHEDULE

Measurement/Event	Day 0	1	2	3	4	5	6	7	14	21	28	90
Demographics, History and Physical	X											
Etiology of ARDS	X											
APACHE III	X											
HCG (females)	X											
Alcohol Use/Smoking History	X											
CXR (number of quadrants)	X											
Study NMB Administration	X	X	X									
Baseline LTO	X											
Non-protocol NMB administration	X	X	X	X	X							
Level of Sedation	X	X	X	X	X	X	X	X				
Sedation Interruption (y/n)	X	X	X	X	X	X	X	X				
Gross motor assessment				X								
ICU Mobility Scale		X	X	X	X	X	X	X	X	X	X	
Ventilator Parameters#†	X	X	X	X	X			X				
Arterial Blood Gases	A	A	A	A	A			A				
K+, HCO 3 , glucose	A	A	A	A	A			A				
Pneumothorax (y/n)*	X										X	
Use of rescue procedures (y/n)*											X	
Fluids (intake/output)	X	X	X	X	X	X	X	X				
Central Venous Pressure	A	A	A	A	A	A	A	A				
On-study meds: sedative, opioid, corticosteroid administration (y/n)	X	X	X	X	X			X				
SOFA Score (modified) B	X	X	X	X	X	X	X	X	X	X	X	
Manual Muscle Testing (with screening)								X	X	X	X	
Paralysis recall assessment**											X	
Plasma Collection	X	X	X									
Urine Collection	X	X	X									
Whole Blood collection for DNA/RNA	X		X									
Vital Status§											X	X

X=Required

A=When available

†= Data gathered at times indicated or until 48 hours UAB, whichever occurs first

\*\*=Collected once during study hospitalization

B=Records clinically available creatinine, platelets, bilirubin, SBP and vasopressor use

~=Data gathered on days 0-28 or until d/c from study hospital

#=Measure during reference period (0600-1000); other values may be obtained closest to 0800 on the specified calendar date

§=Also measure at 6 and 12 months as part of Long Term Outcome.

\*= Assessed for days 1-28 once on day 28 or discharge

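### SAP 2.8 leaves the home-to-death transition out of the 6- and 12-month survival model, although its own worked example uses it

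*SAP*

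**What the plan says.** SAP section 2.8 (Long Term Follow Up Data) calculates 6-month and one-year survival separately by arm from a four-state model. It gives the states and allowed moves as "1-Study Hospital, 2-Other Hospital, 3-Home 4-Dead, with possible transitions of 1-2, 1-3, 1-4, 2-3, 2-4".

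The same paragraph then explains the estimation by example: "suppose a patient went home at 100 days but only has 120 follow up at the time of analysis" (or is lost to follow-up at that point). That patient's probability of death is said to be the "probability of a transition from 3 to 4, for a patient who has been home for 20 days".

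The survival estimates feed a between-arm comparison: "The test of a treatment effect will then be the difference in the survival estimates divided by the pooled standard error".

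The protocol plans to collect the deaths that this transition would use. In section 6.4, on the telephone interviews: "The assessments after follow-up will provide information about post-discharge deaths faster than is available from other sources", and "the National Death Index will be used to verify date of death whenever possible". The same section adds: "We will also verify duration of survival for patients lost to follow-up or noted to have died". In the Time-Events Schedule (Appendix B), the footnote to the vital status row reads: "Also measure at 6 and 12 months as part of Long Term Outcome".

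**The concern.** A multistate model is defined by its states and its allowed transitions. With no transition out of state 3, Home is absorbing and the model cannot register a death there. The example relies on a probability that the list fixes at zero, so the two statements cannot both describe the model.

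If the list is programmed as it stands, deaths after discharge home cannot enter the estimates. Six- and 12-month survival is then too high in both arms, and any treatment effect on death after returning home disappears from the planned test.

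**Working it through.** **1. Exits from each state under the list**

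| State | Listed exits |
|---|---|
| 1 Study Hospital | to 2, 3, 4 |
| 2 Other Hospital | to 3, 4 |
| 3 Home | none |
| 4 Dead | none (properly absorbing) |

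**2. Does other text supply 3-4?** Outside section 2.8, no. SAP Appendix A1 has no row for 6- or 12-month survival, Appendix A3 does not define it, and it is not among the seven long-term measures in protocol section 3.9.2. The rule that a patient discharged home is taken to be alive (SAP 2.2 and Appendix A3) is stated for the primary outcome at day 90 only. It does not make an absorbing Home state a convention for 6 or 12 months.

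**3. The SAP's own example patient** (home at day 100, last seen at day 120; 6 and 12 months taken as days 180 and 365). No assumed rate is needed:

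- Remaining time to 6 months: 180 − 120 = 60 days
- Remaining time to 12 months: 365 − 120 = 245 days
- Under the list, the death probability over both intervals is exactly 0. Under the example it is the 3-to-4 probability for someone already home 20 days.

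**4. Error in the survival estimate.** With Home absorbing, everyone who dies after reaching home is counted as alive, so

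overstatement at time t = P(reached home, then died by t).

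This holds whatever deaths occur in facilities after day 90. A daily four-state Markov model run over 365 days, with two sets of arbitrary rates and facility deaths allowed after day 90, gave listed-model survival minus true survival of 0.0731 and 0.1440. Each equalled P(home, then dead). That confirms the identity only; it says nothing about the rates in this trial.

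**5. Illustration of size at 12 months.** Write the overstatement as S × g × h:

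- S = 1 − planning mortality before discharge home to day 90 = 1 − 0.35 = 0.65 (control) and 1 − 0.27 = 0.73 (neuromuscular blockade), from SAP 1.6. This is an upper bound on the share who reach home alive.
- g = share of S who reach home, **assumed** 0.5 to 1.0.
- h = risk of death after home by month 12, **assumed** 0.05 to 0.20.
- Patients per arm at the maximum sample size: 1408 / 2 = 704.

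| | Low end | High end | Deaths omitted per 704 |
|---|---|---|---|
| Control | 0.65 × 0.5 × 0.05 = 1.6 points | 0.65 × 1.0 × 0.20 = 13.0 points | about 11 to 92 |
| Neuromuscular blockade | 0.73 × 0.5 × 0.05 = 1.8 points | 0.73 × 1.0 × 0.20 = 14.6 points | about 13 to 103 |

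**6. Effect on the between-arm difference**

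- With g and h equal in both arms: (0.73 − 0.65) × g × h = 0.08 × 0.025 to 0.08 × 0.20 = 0.2 to 1.6 points too large.
- With h unequal (g = 1 for simplicity), the list gives 0.73 − 0.65 = 8.0 points in every case. If h is 5% in control and 10% with blockade, the true difference is 0.73 × 0.90 − 0.65 × 0.95 = 0.657 − 0.6175 = 4.0 points. With the rates reversed it is 0.73 × 0.95 − 0.65 × 0.90 = 0.6935 − 0.585 = 10.9 points. The error can go either way.

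**The case against.** The strongest reply is that the paragraph largely corrects itself. The worked example names the missing transition and its clock, so a statistician who reads the whole paragraph would be unlikely to program Home as absorbing, least of all in a model meant to give one-year survival and with dated post-discharge deaths in the database. Section 2.8 also says that the duration of each known transition will be calculated, and a death at home is one. On this view it is an editorial slip with little practical risk. The point counts and death counts rest on two assumed inputs and span a wide range, and in the equal-arm case the tested quantity barely moves.

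Most of this stands. The example does show that 3-4 was intended, following it does no harm, and the sizes are illustrations. It does not make the list right, however. The list is the formal statement of the model, and no text outside this paragraph settles the conflict between it and the example. The mild effect on the difference also depends on equal later mortality in the two arms, which is part of what a long-term comparison is meant to examine.

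**Conclusion.** The concern holds, as a minor one. The transition list in SAP 2.8 is wrong as written and contradicts the example beside it; the likely cause is an omission in drafting.

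The one result free of assumptions is that the list gives the SAP's example patient zero risk of death for the 60 days to day 180 and the 245 days to day 365. The bias in the survival estimates cannot be determined from the documents, which give neither a rate of death after home nor the split of discharge destinations. Under the assumed ranges it runs from small (under 2 points) to substantial (13.0 points in control, 14.6 with blockade). If later death differs by arm, neither the size nor the direction of the error in the difference can be judged.

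Only the 6- and 12-month survival analysis is touched. The primary outcome, the sample size and the interim boundaries are not affected.

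**What to change.** In SAP 2.8, add 3-4 to the end of the list of possible transitions, and state that time in this transition is counted from arrival home, as the worked example already implies.

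The cost is one added transition and its clock in one sentence. No new data are needed, because the vital status checks at 6 and 12 months and the National Death Index verification are already planned. No figure stated in either document changes.
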